1.12 Clinical Experience with ABI-009 in Pediatric Participants

ABI-009 is currently being investigated in a multicenter phase 1 study (ADVL1514) by the Children's Oncology Group (COG) in pediatric participants with recurrent or refractory solid tumors. The aims of the trial will be to establish the maximum tolerated pediatric dose of ABI-009 administered as an intravenous infusion over 30 minutes on Days 1 and 8 of a 21-day cycle, in combination with temozolomide and irinotecan (administered on Days 1-5), and to investigate

the toxicities, pharmacokinetics, and pharmacodynamics of ABI-009 in pediatric participants with recurrent or refractory solid tumors, including CNS tumors. The study uses the Rolling Six escalation/de-escalation design, and the starting dose of ABI-009 is 35 mg/m².

As of Jan 30, 2018, 6 participants have been enrolled and received treatment. Overall, the adverse events observed with ABI-009 in pediatric participants are consistent with those observed in previous clinical studies in adults. The main dose limiting toxicity of ABI-009, administered as a single agent and in combination with cytotoxic agents temozolomide and irinotecan, is grade 3 thrombocytopenia (2 out of 5 participants receiving ABI-009 at 35 mg/m²). As per the protocol de-escalation guidelines, the new cohort of participants will receive an ABI-009 dose of 20 mg/m² in combination with temozolomide and irinotecan.

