2.1 Risk / Benefit Assessment

The mTOR inhibitors (rapamycin/sirolimus, temsirolimus and everolimus) as a class have similar side effects and safety profiles and one can refer to the package inserts of the marketed mTOR inhibitors for safety information. No new side effects were noted with ABI-009 (see investigator brochure).

The safety data available in the literature to date for all completed controlled and uncontrolled clinical studies suggest that: (a) mTOR inhibitors are generally well tolerated at both daily and weekly dose schedules, and (b) mTOR inhibitors give a favorable safety profile, with adverse events (AEs) being manageable, reversible, and non-cumulative. Most common adverse reactions (incidence $\geq 10\%$) associated with mTOR inhibitors are stomatitis, rash, fatigue, asthenia, diarrhea, anorexia, nausea, mucosal inflammation, vomiting, pneumonitis, cough, peripheral edema, infections, dry skin, epistaxis, pruritus, and dyspnea. The most common grade 3-4 adverse reactions (incidence $\geq 2\%$) were infections, stomatitis, fatigue, and pneumonitis. Non-infectious pneumonitis is a class effect of rapamycin derivatives, and some of these cases have been severe and on rare occasions, fatal outcomes have been observed.

mTOR inhibitors have immunosuppressive properties and may predispose patients to bacterial, fungal, viral or protozoan infections, including infections with opportunistic pathogens. Localized and systemic infections, including pneumonia, other bacterial infections, invasive fungal infections, such as aspergillosis or candidiasis and viral infections including reactivation of hepatitis B virus, have been described in patients taking mTOR inhibitors. Some of these infections have been severe (e.g. leading to respiratory or hepatic failure) and occasionally have had a fatal outcome.

The most common laboratory abnormalities (incidence $\geq 50\%$) associated with mTOR inhibitors are anemia, hypercholesterolemia, hypertriglyceridemia, hyperglycemia, lymphopenia, and increased creatinine. The most common grade 3-4 laboratory abnormalities (incidence $\geq 3\%$) were lymphopenia, hyperglycemia, anemia, hypophosphatemia, and hypercholesterolemia.

Comprehensive clinical safety data and nonclinical toxicology information are available for long term dosing with rapamycin and other mTOR inhibitors, which have been included in previous regulatory submissions with ABI-009 (IND 125669 and Investigator's Brochure, version 5.0).

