11 ADVERSE EXPERIENCE REPORTING AND DOCUMENTATION

11.1 Adverse Events

An AE is any untoward medical occurrence in a clinical investigation of a participant administered a pharmaceutical product and that does not necessarily have a causal relationship with the treatment. An AE is therefore any unfavorable and unintended sign (including an abnormal laboratory finding), symptom or disease temporally associated with the administration of an investigational product, whether or not related to that investigational product. An unexpected AE is one of a type not identified in nature, severity, or frequency in the current Investigator's Brochure or of greater severity or frequency than expected based on the information in the Investigator's Brochure.

The Investigator will probe, via discussion with the participant, for the occurrence of AEs during each participant visit and record the information in the site's source documents. All AEs are to be collected, from enrollment through end of the subject's study participation, and recorded in the participant CRF. Attribution will be unrelated, unlikely, possible, probably, or definite.

Taking into account the targeted population and the secondary endpoints of the study, Grade 1 and 2 seizures as defined by the National Cancer Institute's Common Terminology Criteria for Adverse Events (CTCAE) v5 will not be tracked as adverse events and will not be included in the baseline patient assessment.

AE Severity

The CTCAE v5 should be used to assess and grade AE severity, including laboratory abnormalities. If the experience is not covered in the modified criteria, the guidelines shown in Table 3 below should be used to grade severity. It should be pointed out that the term "severe" is a measure of intensity and that a severe AE is not necessarily serious.

Table 7. AE Severity Grading

Severity (Toxicity Grade)	Description
Mild (1)	Mild; asymptomatic or mild symptoms; clinical or diagnostic observations only; intervention not indicated
Moderate (2)	Moderate; minimal, local or noninvasive intervention indicated; limiting age-appropriate Instrumental activities of daily living (e.g., preparing meals, using the telephone, managing money)
Severe (3)	Severe or medically significant but not immediately life-threatening; hospitalization or prolongation of hospitalization indicated; disabling; limiting self-care activities of daily living (e.g., bathing, dressing, feeding self, using toilet, taking medications)

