15.3 Analysis of Primary Endpoint - Safety Endpoints

All reported treatment emergent SAEs and AEs will be coded using MedDRA and grouped by body system. Treatment emergent AEs are defined as AEs presenting post study treatment initiation. SAEs and AEs will be tabulated using standard coding terms sorted by body system. The incidence of AEs in each treatment arm will be tabulated by seriousness, severity, and relationship to study drug. If an AE is reported more than once during the study period for a given participant, the greatest severity and the worst-case relationship will be presented in tables.

The number of SAEs and AEs will be summarized as follows: (i) The proportion of participants with at least one (S)AE, (ii) The average number of (S)AEs per participant, and (iii) The rate of (S)AEs per participant week of follow-up. Histograms showing the frequency of the number of (S)AEs in each treatment group will be included. Rates of (S)AEs by System Organ Class (SOC) will be presented by treatment group. Poisson regression modeling will be used to derive rate ratios and 95% CIs for each SOC.

Safety lab data at each study visit and changes from baseline will be summarized by treatment group. In addition, the following clinical laboratory summaries will be presented by treatment group: (i) the incidence of clinically significant abnormalities at each study visit; and (ii) tables summarizing the frequencies of participants below, within, and above the normal reference ranges at baseline and end of study; and (iii) tables displaying baseline to end of study shifts in each laboratory value (shifts between below, within or above normal range).

The number of hospitalization events and proportion of participants hospitalized will be summarized and compared by treatment group. Poisson regression modeling will be used to derive rate ratios and 95% CIs to compare hospitalization rates between treatment groups.

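### The laboratory shift tables compare baseline with an undefined end-of-study value in three normal-range categories, so some grade 3 courses show no shift and no laboratory table gives each participant's worst grade

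*Combined protocol and SAP*

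**What the plan says.** Section 15.3 lists three laboratory summaries by treatment group:

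- Item (i): "the incidence of clinically significant abnormalities at each study visit".
- Item (ii): "tables summarizing the frequencies of participants below, within, and above the normal reference ranges at baseline and end of study".
- Item (iii): "tables displaying baseline to end of study shifts in each laboratory value (shifts between below, within or above normal range".

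The same paragraph opens with a broader commitment: "Safety lab data at each study visit and changes from baseline will be summarized by treatment group". The synopsis repeats all of this by dosing group.

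Other parts of the protocol bear on the point:

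- **Endpoint.** Section 5.1 makes clinically significant abnormal laboratory values during dosing part of the primary safety endpoint.
- **Adverse events.** When an event recurs in a participant, Section 15.3 says that "the greatest severity and the worst-case relationship will be presented in tables". Section 11.1 counts an abnormal laboratory finding as a possible adverse event and adds: "The CTCAE v5 should be used to assess and grade AE severity, including laboratory abnormalities".
- **Dose-limiting toxicity.** Section 8.5 counts grade 3 or higher toxicity that the principal investigator judges definitely or probably related and that occurs within 30 days of dosing.
- **Baseline and end of study.** Section 15.1 defines a baseline period (Days 0-30) but no baseline laboratory value. No section defines the end-of-study laboratory value.

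**The concern.** Items (ii) and (iii) look at the wrong time for the endpoint they serve. The endpoint concerns abnormal values during dosing, while these tables use a value taken after it.

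The protocol's own rules also steer late values towards recovery. Table 4 interrupts drug for grade 3 cytopenia until grade 1 or better. Section 11.4 follows participants who stop for a suspected drug-related abnormality at least weekly until it resolves or returns to grade 1. The risk assessment in Section 2.1 describes mTOR inhibitor toxicity in general "with adverse events (AEs) being manageable, reversible, and non-cumulative". For toxicity of that kind, the worst value says more than the last one.

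The categories also carry no severity. A value that is slightly outside the normal range and one that is grade 3 on the same side fall in the same cell. Section 6.2 admits participants who may already be outside the range, so this can arise from the first sample.

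At stake is whether the published laboratory tables give a fair picture of the worst laboratory toxicity at each dose. Cytopenia is a relevant case. Section 1.11 reports thrombocytopenia as the most common hematologic treatment-related event in the adult single-agent study (58%), and Section 1.12 reports it as the main pediatric DLT.

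**Working it through.** The plan states no figure for these tables, so there is nothing to reproduce. The check applies the stated rule to example courses.

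**Rule.** Category C(x) is below if x < LLN, above if x > ULN, and otherwise within, where LLN and ULN are the lower and upper limits of normal. The table records C(baseline) → C(end of study). It shows no shift exactly when the two categories are equal. Values in between do not enter.

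**Inputs from the documents**

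- Section 6.2: platelets at least 100 and ANC at least 1.0 (both ×10⁹/L); ALT and bilirubin up to 5 times ULN.
- Table 4: grade 3 thrombocytopenia is 25 to below 50, with grade 1 or better from 75. Grade 3 neutropenia is 0.5 to below 1, with grade 1 or better from 1.5.

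**Assumptions.** The documents give no normal limits. LLN is taken as 140 to 160 for platelets and 1.5 to 2.0 for ANC. The courses are illustrations, not forecasts.

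| Course (baseline → worst → last) | Tabulated as | Shift shown? |
|---|---|---|
| Platelets 200 → 40 → 160 or 210 | within → within | No |
| Platelets 120 → 40 → 110 | below → below | No |
| Platelets 120 → 40 → 45 (last value still grade 3) | below → below | No |
| Platelets 200 → 40 → 80 or 110 | within → below | Yes |
| Platelets 100 → 40 → 160 | below → within | Yes, as improvement |
| ANC 2.5 → 0.7 → 2.5 | within → within | No |
| ANC 1.2 → 0.7 → 1.2 | below → below | No |
| ANC 2.5 → 0.7 → 1.6 | depends on LLN | No at 1.5; yes at 1.8 and 2.0 |
| ALT 2 × ULN → 15 × ULN → any value above ULN | above → above | No |

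Every row except the one marked as depending on LLN gives the same result across the assumed range. The ALT row needs no assumed limit, because both entry and worst value are expressed in multiples of ULN. Where a shift does show, it reflects the last value and not the depth of the fall.

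**Which value is last?** Under Appendix 1 the last scheduled CBC is at Visit 6, one week after dosing. Visit 7 laboratory tests are at discretion (Section 10.6), or taken if earlier chemistry or coagulation results were abnormal or there is a clinical indication (Appendix 1). None are listed for Visits 8 and 9. For chemistry, Appendix 1 makes Visit 6 conditional too, although Section 10.5 lists it, so the last unconditional sample in the schedule is at Visit 4. The end-of-study value can therefore fall at different times for different participants and analytes. Those with abnormal results may be sampled later, with more time to recover.

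**The case against.** The strongest reply is that the event is reported elsewhere. Under Sections 11.1 and 15.3 together, a grade 3 platelet count is an adverse event, graded by CTCAE and tabulated at its greatest severity for that participant, whether or not it recovers. The by-visit summaries cover Visits 4 to 6. In a cohort of three, one fall from 200 to 40 moves the mean change by 160/3 ≈ 53 if the other two are unchanged, which is hard to overlook. Related grade 3 toxicity is a DLT, and the DSMB reviews all adverse events before each escalation cohort and before the expansion (Section 14). If the worst CBC is at Visit 6 and no later sample is taken, the end-of-study value is itself the worst sampled value.

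Most of this stands. A reader might infer that a recovered grade 3 cytopenia would vanish from the analysis, or that dose escalation is compromised. The documents do not support either reading, because these other outputs exist and the MTD rule does not use the shift table. Nor can it be said that the tables never display cytopenia, or that every below-normal start gives no shift. The worked courses include exceptions to both.

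The pediatric DLT figure, "grade 3 thrombocytopenia (2 out of 5 participants receiving ABI-009 at 35 mg/m²", should not be read as a forecast for this trial either. It comes from a study combining the drug with temozolomide and irinotecan, and 35 mg/m² is above this trial's highest level of 20 mg/m². The Section 2.1 statement on reversibility is a class statement, not evidence of platelet recovery on this schedule.

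The reply does not fully close the gap. By-visit summaries are not worst value per participant. Clinical significance in item (i) is tied to no grade and is judged open-label. The adverse event table depends on the laboratory value having been recorded as an event. The DLT rule requires definite or probable attribution, so a grade 3 value judged only possibly related does not meet that criterion.

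**Conclusion.** The point holds as a reporting weakness in a primary safety endpoint. The range and shift tables miss two kinds of course: a grade 3 abnormality that returns to its baseline category, and one that starts and ends on the same abnormal side. No planned table shows each participant's worst laboratory grade from the laboratory data alone, independent of judgements about significance or attribution.

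It is not a detection failure and does not affect the MTD decision. Its size cannot be given as a rate, because the documents give no expected frequency of recovered grade 3 values at these doses. The structural conclusion follows from the table definition alone. The platelet and ANC examples rest on the assumed lower limits; the ALT example does not.

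**What to change.** In Section 15.3, the synopsis and the SAP promised in Section 15.1:

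1. Make the main laboratory shift table run from the last pre-Dose-1 CTCAE grade to the worst post-dose CTCAE grade, by dose group, in both directions where an analyte can be abnormal either way. Grades should be computed from the laboratory values.
2. Keep the baseline to end-of-study table as a recovery summary, and define its end point by analyte. For the CBC this is Visit 6, with Visit 7 only if indicated. For chemistry, first reconcile Section 10.5 with Appendix 1.
3. Name one CTCAE version. Section 3.1 cites 4.03, while Sections 8.6 and 11.1 cite version 5.

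Timing of the lowest or highest value is optional. The worst grade will cover only samples actually taken, so the table should state how many participants contribute at each visit.

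The cost is a little extra table programming and wording. The data are already collected, and no participants or visits are added.

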15.4 Analysis of Primary Endpoint – Tolerability (Study Drug Discontinuation and Compliance)

The proportion of participants permanently discontinuing study drug will be tabulated by treatment group. Drug discontinuation events will be categorized as: (1) Permanently discontinued study drug and (2) Permanently discontinued study drug and withdrew from study. The reason for permanent drug discontinuation will be summarized.

Treatment compliance will be assessed via compliance with scheduled weekly infusions.

15.5 Analysis of Secondary Endpoints

Efficacy is defined as the change in seizure frequency between baseline and follow-up expressed as **percentage reduction in seizure rate** (reduction in seizure frequency from baseline, calculated as (Baseline frequency [seizures/week] – frequency at follow-up [seizures/week])/Baseline frequency [seizures/week]) and **median percentage reduction** in seizure frequency. **Treatment response rate** will be defined as the proportion of participants achieving at least a 25% reduction in seizure frequency from baseline. **Seizure frequency** will be defined as the ratio between the number of seizures and the number of days on which seizure information was known within the same period of time (for either baseline or maintenance phase). Additional secondary endpoints will include **frequency of seizure-free days** during the maintenance period, **seizure-free rate** (participants remaining seizure free during the maintenance period), and rapamycin **blood level–response relationship** analysis. These endpoints will be analyzed using appropriate statistical tests, such as the t-test and ANOVA.

Quality of Life for Children with Epilepsy Parent Form (QOLCE) [1] and Nisonger Child Behavioral Rating Form (NCBRF) [2,3] scores will be compared using appropriate statistical tests for ordinal data, including Wilcoxon signed rank tests, logistic regression, or contingency tables.

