	
[seizures/week])/Baseline frequency [seizures/week]) and median percentage reduction in seizure frequency. Treatment response rate will be defined as the proportion of participants achieving at least a 25% reduction in seizure frequency from baseline. Seizure frequency will be defined as the ratio between the number of seizures and the number of days on which seizure information was known within the same period of time (for either baseline or maintenance phase). Additional secondary endpoints will include frequency of seizure-free days during the maintenance period, seizure-free rate (participants remaining seizure free during the maintenance period), and rapamycin blood level-response relationship analysis. These endpoints will be analyzed using appropriate statistical tests, such as the test of proportions and time to event analyses.
 
Quality of Life for Children with Epilepsy Parent Form (QOLCE) [1] and Nisonger Child Behavioral Rating Form (NCBRF) [2, 3] scores will be compared using appropriate statistical tests for ordinal data, including Wilcoxon signed rank tests, logistic regression, or contingency tables.

Rationale for Number of Participants	In this phase 1 study, it is estimated that a maximum of up to 18 participants will be required to achieve the MTD; however, MTD could be reached with as few as 9 participants, but also possible that the MTD is not reached in this study. With the MTD expansion cohort, it is estimated that additional 6 participants would bring the maximum number of participants enrolled to 18. A total of up to 18 participants should be enough for a safety and tolerability study in an orphan condition.

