4 STUDY DESIGN

4.1 Study Overview

This is a prospective, single-center, non-randomized open-label phase 1 study to investigate multiple dose levels of ABI-009 for surgically-refractory epilepsy. Up to 18 participants are planned to be enrolled into the study.

The duration of participation for each participant is up to 18 weeks, including a 4-week baseline period to obtain baseline outcome rates, a 3-week active study period and a 12-week follow-up period (see Figure 1). After the baseline period, participants will be started on the assigned dose of ABI-009, given once weekly for a total of 3 weeks. Dose levels to be tested are below:

For dose finding, ABI-009 will be tested in cohorts of 3 participants each using the standard 3+3 dose-finding design. Initial starting dose will be at 5 mg/m²/week.

Table 3: ABI-009 Cohort Dosing Schedule

Dose levels	ABI-009 in mg/m ²
-2	1
-1	2.5
1	5
2	10

3	20
---	----

Escalation to the next dose level with a new cohort of 3 participants will occur after no DLT was observed. There will be no intra-participant dose escalation allowed. If a DLT occurs in a cohort, an additional 3 participants will be recruited to the cohort. If no further DLTs occur, then a new cohort of 3 participants at the next higher dose level can be enrolled. If 2/6 participants at a dose level experience a DLT, then the cohort will be closed to further enrollment and 3 participants will be enrolled at the next lower dose level, and so on. The MTD is the highest dose level in which ≤ 1 participant has a DLT. There will be no intra-participant dose escalation allowed.

Once the MTD has been determined, the MTD cohort will be opened for an estimated additional 6 participants. These participants will adhere to the identical protocol of the rest of their cohort.

Product will be administered IV every 7 days for 3 weeks.

For a detailed review of visits, please see Appendix 1.

Total duration of the study is expected to be about one year.

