5.2 Secondary Endpoints

I. Efficacy

- Seizure frequency
- Percentage reduction in seizure frequency
- Median percentage reduction in seizure frequency
- Response rate
- Frequency of seizure-free days
- Seizure-free rate
- Rapamycin blood level–response relationship

II. Quality of life and behavioral changes

- Quality of Life for Children with Epilepsy Parent Form (QOLCE) [1] and

- Nisonger Child Behavioral Rating Form (NCBRF) [2,3]
- Both will be completed at baseline, at the completion of maintenance, and at the completion of the 3-month follow-up period.

III. Weekly whole blood rapamycin trough levels for three consecutive weeks.

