15 STATISTICAL METHODS AND CONSIDERATIONS

15.1 General Considerations

Prior to the analysis of the final study data, a detailed Statistical Analysis Plan (SAP) will be written, describing all analyses that will be performed. The SAP will contain any modifications to the analysis plan described below.

For the purposes of analyses, baseline period will be defined as Days 0-30. Except where otherwise noted, comparisons of continuous variables between pre and post treatment periods will utilize t-tests or linear regression, test of proportions and analysis of count data using Poisson regression. Except where otherwise noted, all tests will be two-sided and statistical significance will be determined at the 0.05 level. Missing data methods for the primary and key secondary endpoints will be described in the SAP. No adjustment for multiple comparisons will be made.

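### For the rapamycin level–response endpoint the plan names no method that uses trough and seizure change as continuous measures; one should be pre-specified

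*Combined protocol and SAP*

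**What the plan says.** The level–response relationship is a secondary endpoint in Section 5.2, the synopsis and Section 15.5. The exposure data are described in Section 5.2: "Weekly whole blood rapamycin trough levels for three consecutive weeks". Section 15.5 then covers percentage reduction, response rate, seizure-free days, seizure-free rate and level–response with one sentence: "These endpoints will be analyzed using appropriate statistical tests, such as the t-test and ANOVA". The synopsis covers the same list with another: "These endpoints will be analyzed using appropriate statistical tests, such as the test of proportions and time to event analyses".

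Linear regression is mentioned in Section 15.1, but for a different purpose: "comparisons of continuous variables between pre and post treatment periods will utilize t-tests or linear regression". The same section sets the error rate, "all tests will be two-sided and statistical significance will be determined at the 0.05 level", and states "No adjustment for multiple comparisons will be made". It also says that a detailed SAP will be written before the final analysis and will hold any modifications.

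No text says which trough summary enters the level–response analysis, which response measure and window are used, or how either would be grouped. Section 3.3 lists relationships between efficacy and trough levels a second time, as exploratory, also without a method.

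**The concern.** Trough (ng/mL) and change in seizure frequency are both continuous. A t-test or ANOVA compares means between groups, so one of the two must be cut first. A test of proportions needs both cut. A time-to-event model could take trough as a continuous covariate, but it replaces seizure change with the time to an event that is not defined.

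Two things are at stake. Cutting a continuous variable discards information that a study of at most 18 people can ill afford. And with no trough cut-point stated, two differing lists of tests and no multiplicity adjustment, several splits could be tried after the data are seen.

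The groups already in the protocol do not solve this. ANOVA by dose level tests dose, not trough. Section 1.13 reports troughs of 4.3–9.1 ng/ml at 5 mg/m² and 7.3–17.5 ng/ml at 10 mg/m² (three participants in another study), so exposure overlaps between neighbouring doses. Continued enzyme-inducing AEDs (8.6.1) and dose reductions for toxicity (8.6) can add variation within an assigned dose level.

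**Working it through.** The plan states no power, effect size or correlation for this endpoint, so there is no figure of its own to reproduce.

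**Inputs from the documents**
- Maximum n = 18: "Up to 18 participants are planned to be enrolled into the study" (4.1).
- Smaller n is possible. Three cohorts of 3 with no DLT plus the expansion of 6 give 3 × 3 + 6 = 15. The synopsis adds "MTD could be reached with as few as 9 participants".
- Two-sided alpha of 0.05 (15.1).

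**Assumed inputs:** true correlation ρ between log trough and response, bivariate normal data, and the share of responders.

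**Method.** Simulation with 40,000 replicates per setting. The regression slope test is t = r√(n−2)/√(1−r²) on n−2 degrees of freedom. It is compared with a t-test of response at a median split of trough, one-way ANOVA of response on trough tertiles, and a t-test of trough between responders and non-responders.

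**Power at n = 18 (loss in percentage points against regression)**

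| ρ | Regression | Median-split t | Tertile ANOVA | Responder t, 35% responders |
|---|---|---|---|---|
| 0.3 | 0.228 | 0.156 (7.2) | 0.141 (8.8) | 0.153 (7.5) |
| 0.4 | 0.394 | 0.249 (14.5) | 0.225 (16.9) | 0.244 (15.0) |
| 0.5 | 0.587 | 0.379 (20.8) | 0.350 (23.7) | 0.367 (22.0) |
| 0.6 | 0.789 | 0.546 (24.3) | 0.526 (26.3) | 0.530 (25.9) |
| 0.7 | 0.932 | 0.730 (20.2) | 0.728 (20.4) | 0.704 (22.8) |
| 0.8 | 0.992 | 0.897 (9.5) | 0.909 (8.3) | 0.867 (12.5) |

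At ρ = 0 all four tests reject in 0.049 to 0.051 of runs, so the comparison is fair.

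**Hand check at ρ = 0.6.** Fisher's z gives power ≈ Φ(atanh(ρ)√(n−3) − 1.96).
- Regression: Φ(0.693 × 3.873 − 1.96) = Φ(0.72) = 0.77.
- Median split: splitting a normal variable at its median multiplies the correlation by √(2/π) = 0.798, so ρ becomes 0.6 × 0.798 = 0.479. Power is Φ(0.521 × 3.873 − 1.96) = Φ(0.06) = 0.52.
- The loss is about 24 points, in line with the simulated 24.3.

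**Other settings**
- n = 15, ρ = 0.5, 0.6, 0.7: median split loses 19.1, 24.9, 25.4; tertile ANOVA loses 22.3, 27.7, 26.5.
- n = 9, same ρ: median split loses 11.6, 19.1, 27.9; tertile ANOVA loses 14.1, 22.8, 31.8. Regression itself has power of only 0.287, 0.432, 0.616.
- n = 18 with 20% responders, same ρ: the responder t-test loses 30.0, 38.0, 38.2.
- n = 18, ANOVA by dose level (6/6/6 or 3/3/12 participants, within-dose CV of trough 30% or 50%, all assumed), ρ = 0.4 to 0.7: loss of 17 to 43.

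**The case against.** A reader might infer that the plan requires trough or response to be cut. It does not. The tests are examples in one sentence that serves endpoints of several types, nothing assigns the t-test to this endpoint, and the SAP is still to come. That stands, and it limits the finding to a method left open and described differently in two places.

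A reader might also infer that no cut-point exists. For response one does: Section 15.5 defines a responder by a reduction of at least 25%. Only a trough cut is missing. Using the responder definition still loses power, as the table shows.

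The size of the loss rests on assumptions. Bivariate normal data favour linear regression. In a smaller simulation (3,000 runs, n = 18, 40% responders assumed), Spearman's correlation had power 0.51, 0.73 and 0.88 at ρ = 0.5, 0.6 and 0.7. The better t-test had 0.38, 0.55 and 0.73. A rank method therefore still gains 13 to 18 points, less than regression but not nothing.

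Finally, it is tempting to call this analysis the trial's main internal evidence of drug effect. The documents do not support that. Dose follows enrolment order without randomisation (8.1), trough may be confounded with enzyme-inducing AEDs (8.6.1), and Section 3.3 also lists the relationship as exploratory. Regression removes none of these limits.

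**Conclusion.** The point holds as one of specification. Section 15.5 and the synopsis name different tests for this endpoint, and none of them relates continuous trough to continuous seizure change. If the named t-test or ANOVA is applied with a median or tertile split, about 20 to 26 points of power are lost against linear regression at n = 18 and an assumed correlation of 0.5 to 0.7, and about 14 to 17 at 0.4.

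A single fixed loss should not be read into this. The documents supply no correlation, 18 is a ceiling, and over all the groupings tried at n = 18 with ρ from 0.3 to 0.8 the loss runs from about 7 to 43 points. The sample size rests on feasibility and the 3+3 design (15.6), so no design figure changes. The change is worth making because it costs little and closes off a choice of cut-point after the data are seen.

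**What to change.** In Section 15.5 and the synopsis, take the level–response endpoint out of the group-test sentences and put the same statement in both, carried into the SAP:

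- **Response:** the participant's percentage change in seizure frequency as already defined, with the window named. The log ratio of post-dose to baseline frequency is an alternative, but then the handling of zero counts must be stated.
- **Exposure:** log of the participant's mean post-dose trough, used as a continuous variable across all dose levels. Name the visits. Section 10.4 lists a trough draw at the first dosing visit, before any drug, while Appendix 1 does not.
- **Method:** linear regression, reporting the slope with its 95% CI, and Spearman's correlation as the robustness check.
- **Status:** supportive only, with assignment by enrolment order and possible confounding with enzyme-inducing AEDs stated as limits.

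The cost is one sentence of wording and an assumption of linearity on the log-trough scale, which Spearman's correlation checks. The analysis uses troughs and diaries already collected, with no added burden on participants.
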